5.2 Baseline values

The **baseline value** is defined to be the last non-missing value which was assessed before the first dose of investigational treatment.

5.3 Calculation of durations

Durations in months will be calculated as durations in days by dividing by 30.4375.

Time from initial diagnosis will be calculated in years, from the date of initial diagnosis to the date of the first dose date: (first dose date – date of initial diagnosis) /365

Total treatment duration will be calculated in days as:

- If last cycle is Cycle 1, 2, 3 or 4: last dose date first dose date + 7
- If last cycle is Cycle 5 or later: last dose date first dose date + 21

5.4 Missing data

Imputation of partial start date for Adverse Event and Medications

- if month and may are missing, and the year is same as the year of first dose, then assign the date of first dose as AE start date; else assign Jan 1st of the year.
- if only day is missing, and the month and year are same as the month and year of first dose, then assign the date of first dose as AE start date; else assign 1st day of the month.
- Compare the imputed date with the date of last known alive/contact; if the imputed date is bigger than the date of last known alive/contact, then assign the date of last known alive/contact as AE start date.

Imputation of partial end date for Adverse Event/Medications, and partial date of diagnosis:

- assign DEC 31st of the year if both Month and Day are missing.
- assign last day of the month if only Day is missing.
- Compare the imputed date with the date of last known alive/contact; if the imputed date is bigger than the date of last known alive/contact, then assign the date of last known alive/contact as AE end date.

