5.5 Observation and analysis times

Subject information may be presented by cycle day or study day, as appropriate.

Study days

Study day is defined as the number of days between the first dose of trial medication and a particular date, and is calculated as:

- Study day = Assessment date Date of first dose of trial medication, where assessment date is before the date of first dose
- Study day = Assessment date Date of first dose of trial medication + 1, where assessment date is on or after the date of first dose

Therefore, the date of the first dose of trial medication will be Day 1, and the day immediately prior will be Day -1.

Trial periods

For the Escalation Part only, the DLT period is defined as the first 21 days of treatment, as per protocol 7.1. Therefore, this period will run from Cycle 1 Day 1 through Cycle 1 Day 21.

The trial participation period is divided into three mutually exclusive segments:

- The pre-treatment period includes information collected from the date of informed consent until the day prior to the first dose of trial medication. (Subjects not receiving trial medication will remain in the pre-treatment period for the duration of their participation.)
- The on-treatment period begins on the date of the first dose of trial medication and continues through the 30th day after the last dose of trial medication (i.e. if the last dose was on Day 1, the on-treatment period would continue through Day 30). The 30th day after last dosing is planned to coincide with the Safety Follow-up Visit.
- The post-treatment period begins at end of the on-treatment period + 1 day

If incomplete data makes it impossible to definitively assign an observation to one of these periods, the data will be conservatively assigned to the on-treatment period.

6 Subject Accounting and Disposition

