7.2 Disease characteristics

The following disease diagnosis will be presented:

- Primary diagnosis at Screening (uterine, prostate, etc.)
- Time from initial diagnosis to 1st dose (years)

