9.2 Adverse events (AEs)

AEs will be coded using MedDRA, and the National Cancer Institute Common Terminology Criteria for AEs (CTCAE criteria v5.0). Subjects will be included only once in incidence summary tables, presented by Preferred Term (PT) only.

- Adverse events collected during the pre-treatment period (see definition in Section 5.5) will be considered pre-treatment and included in listings (marked with a flag).
- Treatment-emergent adverse events (TEAEs) are defined as AEs which begin, or worsen, during the on-treatment period.
- Adverse events collected during post-treatment period may be tabulated separately from the TEAEs and provided in listings (marked with a flag).

The following summaries of TEAEs will be presented:

- TEAE overview
- TEAEs by PT, in order of descending frequency
- TEAE by SOC, PT and Worst Toxicity Grade, in order of descending frequency
- Related TEAEs, by PT, in order of descending frequency
- TEAE Leading to Withdrawal from Treatment by SOC, PT and Worst Toxicity Grade, in order of descending frequency
- Serious TEAEs, by PT, in order of descending frequency
- Fatal TEAEs (TEAEs resulting in death) by PT, in order of descending frequency

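### SAP 5.4 imputes partial diagnosis dates as late as possible with no cap at first dose, so time since diagnosis can be negative; two smaller date rules in 5.4 and 5.5 also need tidying

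*SAP*

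**What the plan says.** SAP 5.4 holds two lists of imputation rules.

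The second list is introduced as "Imputation of partial end date for Adverse Event/Medications, and partial date of diagnosis". Its first instruction is to "assign DEC 31st of the year if both Month and Day are missing". If only the day is missing, the last day of the month is used. A final bullet pulls the imputed date back to the last known alive/contact date if it falls later. That bullet names only the AE end date, but it sits in the list that covers diagnosis, so I apply it to diagnosis as well. Neither first dose nor consent appears as a limit.

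The imputed diagnosis date feeds SAP 5.3: "Time from initial diagnosis will be calculated in years, from the date of initial diagnosis to the date of the first dose date". The result is reported as a disease characteristic under SAP 7.2.

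The first list covers partial start dates of AEs and medications. When only the day is missing and the month and year match first dose, "then assign the date of first dose as AE start date; else assign 1st day of the month". The rule for a missing month and day works the same way by year. The only check is again against last known alive/contact; a recorded end date is not consulted.

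SAP 9.2 states: "Treatment-emergent adverse events (TEAEs) are defined as AEs which begin, or worsen, during the on-treatment period". It also states: "Adverse events collected during the pre-treatment period (see definition in Section 5.5) will be considered pre-treatment". In 5.5 the pre-treatment period "includes information collected from the date of informed consent until the day prior to the first dose of trial medication". The same section sends an observation to the on-treatment period only where incomplete data prevent a definite assignment.

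SAP 5.5 also runs the on-treatment period through the 30th day after last dose, and illustrates this with a last dose on Day 1 and an end on Day 30. Protocol 11.5.3.1 ends the period 30 days after last dose.

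**The concern.** A late-date rule is reasonable for the end of an event, where a longer duration is the cautious choice. A diagnosis must come before treatment, so pushing it late can carry it past first dose and give a baseline variable a value that cannot exist. Even a few negative values would pull down the mean and set the minimum of that variable in small dose cohorts.

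The start-date rule has a related gap. An AE caused by a screening procedure that ended before first dose, but has a partial start date, can be given a start on the day of first dose. Its start then falls after its end and, on the start date alone, it meets the TEAE definition.

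For the on-treatment window, a programmer who follows the example instead of the rule would classify an AE starting on the 30th day after last dose as post-treatment.

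**Working it through.** The check is date arithmetic with the SAP's own rules. The documents give no subject dates, so I assume a first dose on 15 March 2021.

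**The one figure the SAP states: Day 30.** SAP 5.5 makes the date of first dose Day 1 and computes study day on or after first dose as assessment date minus first dose date plus 1.
- Counting the dosing day as the first of 30 days: 15 March + 29 days = 13 April, study day 29 + 1 = 30. This reproduces the example, but it is the 29th day after the dose.
- Following the rule as worded: 15 March + 30 days = 14 April, study day 30 + 1 = 31.

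The example is one day short of its rule.

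**Diagnosis date.** Time in years = (first dose date - imputed diagnosis date) / 365, where the imputed date is the end of the known year or month, or last contact if that is earlier.

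| Recorded diagnosis | Last contact (assumed) | Imputed date | Days | Years |
|---|---|---|---|---|
| 2021 | on or after 31 Dec 2021 | 31 Dec 2021 | -291 | -291/365 = -0.80 |
| 2021 | 30 Sep 2021 | 30 Sep 2021 | -199 | -199/365 = -0.55 |
| March 2021 | on or after 31 Mar 2021 | 31 Mar 2021 | -16 | -16/365 = -0.04 |
| 2020 | any later date | 31 Dec 2020 | +74 | 74/365 = +0.20 |

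The last row marks the limit of the problem. If the known year is before the year of first dose, the value is short but possible. The value is negative only when the known year or month is that of first dose and last contact is after first dose. It would be exactly zero if first dose itself fell on the last day of that year or month. With a cap at first dose, the first three rows become 0.

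**AE start date.** Take an AE with start March 2021 (day missing) and a recorded end of 10 March 2021.
- Month and year match first dose, so the imputed start is 15 March, study Day 1.
- The recorded end is study day 10 March - 15 March = -5.
- The start falls 5 days after the end.
- By start date the AE is treatment-emergent. By its recorded end it lies wholly before first dose.

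If the imputed start may be no later than the recorded end, the start is at the latest Day -5 and the AE stays pre-treatment. Medications share the start-date rule, so the same inversion can occur there.

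**The case against.** **Diagnosis.** Protocol 5.1 requires escalation subjects to have progressed on standard therapy, or to be intolerant of it or ineligible for it. A diagnosis in the month of first dose is therefore improbable, and one in the same calendar year is not common. That stands and limits the number of records. A reader might take -0.80 years as the size of the error. It is not a fixed figure, because it needs a last contact on or after 31 December 2021, and the last-contact cap shrinks it otherwise. The sign does not change while last contact is after first dose.

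**AE start.** SAP 9.2 already calls AEs collected before treatment pre-treatment, and the 5.5 fallback reaches only data that cannot be placed. Read together, they point to pre-treatment for an AE with a complete end date before first dose. This largely stands. A reader might infer that the SAP requires such an AE to be counted as a TEAE; the documents do not say that the imputed start overrides those two statements. What is left is an unstated precedence and a start date after its own end in the listings.

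**Day 30.** Protocol 7.1 describes the DLT period as lasting until 7 days after the first full dose, yet for a full dose on C1D15 it ends on Day 21, whereas 15 + 7 = 22. That counts the dosing day as day 1, and on that convention Day 30 would be right. Counting is therefore not uniform across the documents. For SAP 5.5, however, the wording of the rule and the SAP's study-day formula both give Day 31. This agrees with the plain reading of protocol 11.5.3.1 and with the safety follow-up visit at 30 (+14) days in protocol 8.1.1, with which SAP 5.5 plans that day to coincide.

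**Programming checks.** SAP 1.1 places programming notes in the DPS, which is not among the documents. Date-order checks may exist there.

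**Conclusion.** The diagnosis-date rule is wrong as written: it produces an impossible negative time since diagnosis under the conditions shown. In the illustration the value runs from -0.04 to -0.80 years, depending on what part of the date is known and on last contact. The first-dose and last-contact dates are assumptions, and the documents give no count of partial dates.

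The other two points are secondary. The start-date rule lacks a check against a recorded end, which calls for a clarification. The 5.5 example and rule differ by one day and need reconciling.

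A reader might go further and infer that the reported TEAE counts or the DLT findings are unreliable. The documents do not support that. Protocol 9.1.3 makes a condition arising between consent and first dose an AE only if it was caused by a required procedure, so affected AEs should be rare. An AE that ended before first dose could not be a DLT, which must be at least possibly related to GEN1044. The Day 30 example matters only if it is programmed in place of the rule. The effect is confined to descriptive summaries, and this is a minor correction worth making.

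**What to change.** Change three places in the SAP.

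- **5.4, diagnosis.** Cap the imputed diagnosis date at the first-dose date or, more tightly, at informed consent. Protocol 9.1.2 has the diagnosis recorded at screening, so the consent cap avoids implying a diagnosis on the dosing day.
- **5.4, start dates.** For AEs and medications alike, state that when a recorded end date precedes first dose, the imputed start is no later than that end (simplest: equal to it). State that such an AE stays pre-treatment, consistent with 9.2 and the 5.5 limit. Keep the present rule otherwise.
- **5.5, example.** Change Day 30 to Day 31, with a note that protocol 7.1 counts the dosing day as day 1 for the DLT period, so that the two conventions are not confused.

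The cost is three lines of text and the matching programming. No new data are needed.

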5.5 Observation and analysis times

Subject information may be presented by cycle day or study day, as appropriate.

Study days

Study day is defined as the number of days between the first dose of trial medication and a particular date, and is calculated as:

- Study day = Assessment date Date of first dose of trial medication, where assessment date is before the date of first dose
- Study day = Assessment date Date of first dose of trial medication + 1, where assessment date is on or after the date of first dose

Therefore, the date of the first dose of trial medication will be Day 1, and the day immediately prior will be Day -1.

Trial periods

For the Escalation Part only, the DLT period is defined as the first 21 days of treatment, as per protocol 7.1. Therefore, this period will run from Cycle 1 Day 1 through Cycle 1 Day 21.

The trial participation period is divided into three mutually exclusive segments:

- The pre-treatment period includes information collected from the date of informed consent until the day prior to the first dose of trial medication. (Subjects not receiving trial medication will remain in the pre-treatment period for the duration of their participation.)
- The on-treatment period begins on the date of the first dose of trial medication and continues through the 30th day after the last dose of trial medication (i.e. if the last dose was on Day 1, the on-treatment period would continue through Day 30). The 30th day after last dosing is planned to coincide with the Safety Follow-up Visit.
- The post-treatment period begins at end of the on-treatment period + 1 day

If incomplete data makes it impossible to definitively assign an observation to one of these periods, the data will be conservatively assigned to the on-treatment period.

6 Subject Accounting and Disposition

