#### 7 DOSE MODIFICATIONS AND SAFETY MANAGEMENT GUIDELINES

# 7.1 **Dose-Limiting Toxicity**

The DLT evaluation period is defined as the period from the start of the first GEN1044 administration on C1D1 of the Dose Escalation part of the trial until 7 days after the first full dose. As described in Section 4.1, if a subject receives the priming dose on C1D1, one intermediate dose on C1D8, and the full dose starting on C1D15, the DLT period will be the first 21 days of Cycle 1 (Cycle 1 days 1 through 21). If a subject receives the priming dose on C1D1, the first intermediate dose on C1D8, the second intermediate dose on C1D15, and the first full dose on C2D1, the DLT period will be Cycle 1 up to and including C2D7 (ie, a total of 28 days). The DLT evaluation period may be adjusted for potential GEN1044 treatment delay as described in Section 11.1.7.

National Cancer Institute (NCI) Common Terminology Criteria for Adverse Events (CTCAE) v5.0 (NCI-CTCAE, 2017) will be used to assess toxicities/AEs, except for CRS and immune effector cell-associated neurotoxicity syndrome (ICANS) (see Section 10.4.1 and Section 10.4.2, respectively).

A DEC is set up for the study. The DEC will review data from each DL cohort and make a decision regarding dose escalation. That decision of the DEC has to be confirmed by the sponsor SC. The DMC will review data on a quarterly basis.

Events to be collected and assessed by the DMC for DLTs include: SAEs; AESIs where applicable; and clinically significant abnormal laboratory values (that are not already covered by a separate AE term).

The occurrence of any of the toxicities outlined in this section will be considered a DLT if assessed by the investigator to be at least possibly related to GEN1044. AEs clearly not related to the trial treatment (GEN1044) such as disease progression, environmental factors, unrelated trauma, etc, should not be considered a toxicity event.

The following will qualify for a DLT:

- ≥ Grade 3 CRS, graded according to American Society for Transplantation and Cellular Therapy (ASTCT) criteria (Lee et al., 2019) (see Section 10.4.1, Table 16).
- \geq Grade 3 ICANS, graded according to the criteria specified in Table 17, Section 10.4.2.
- Any Grade 3 or 4 non-hematologic toxicity except for:
  - Grade ≥ 3 nausea/vomiting or diarrhea <72 hours with adequate anti-emetic and other supportive care
  - Grade  $\geq$  3 fatigue  $\leq$ 1 week

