#### 11.1.7 Dose-Determining Analysis Set – Dose Escalation Part

The dose-determining set (DDS), which is used to define the number of DLT evaluable subjects on a DL cohort, will include all FAS subjects in the escalation part who meet the exposure criterion (defined below) and have sufficient safety evaluations, or experience a DLT prior to the 2nd full dose administration. The DLT period will extend until 7 days after the first full dose (see Section 4.2).

A subject meets the exposure criterion if all doses, up to and including the 1st full dose, are administered in a timely fashion: In general, the individual doses should not be delayed more than 7 days. However, longer dose delays might be acceptable if the DEC considers the assessments still to be appropriate. The first full dose should be administered at latest by 30 calendar days after C1D1 (if one intermediate dose is administered), or by 38 calendar days after C1D1 (if two intermediate doses are administered), counting the day of first exposure as C1D1.

If there is a longer dose delay the subject is considered as non-DLT evaluable (as long as the reason for the dose delay, or the dose delay itself, is not classified as a DLT). DLTs occurring beyond the DLT period will be presented, but not contribute to the DLT rates for the DL cohort per mBOIN.

Subjects who do not experience a DLT will be considered to have sufficient safety evaluations if they have been observed for  $\ge 21$  days (or  $\ge 28$  days if 2 intermediate doses are applied) following the priming dose, and are considered by both the sponsor and investigators to have enough safety data to conclude that a DLT did not occur.

For a period-specific dose level (doses up to and including 1st full dose), a subject is considered as DLT evaluable if the dose was timely administered (ie, not delayed for more than 7 days) and had sufficient safety evaluations up to the subsequent dose administration to conclude if a DLT did occur or not. The relative DLT periods for priming and intermediate doses extend the planned timing of the subsequent dosing (ie, extends until 7 days after the dose administration). For the 1st full dose, it extends up to 7 days past drug administration. Appendix 9 provides a comparison of the DDS considerations and a template for the reporting of DLT rates.

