3.4 Treatment assignment

Subjects will be enrolled into pre-defined dose cohort during the Escalation Part.

4 Analysis Sets

Enrolled Subjects

Enrolled Subjects include all subjects whose treatment were assigned.

Full Analysis Set (FAS)

The full analysis set (FAS) and safety set are defined in the same way and will comprise all subjects who receive at least 1 dose of trial drug. All subjects will be classified according to the dose level and treatment schedule (if applicable) which they were assigned.

Safety Set (SAF) / Treated Set

The Safety set is the same as the FAS.

Dose-Determining Analysis Set (DDS)

The Dose-Determining Set (DDS) includes all FAS subjects in the Escalation Part who meet the minimum exposure criterion and have sufficient safety evaluations or experience a DLT during the first 21 days of dosing (i.e., in Cycle 1).

A subject will meet the minimum exposure criterion if the subject takes at least 2 out of 3 pre-planned doses during the DLT period (such as 1 priming dose and 1 full dose).

A subject will have sufficient safety evaluations if the subject has been observed for \geq 21 days following the first dose and are considered by both the sponsor and investigators to have enough safety data to conclude that a DLT did not occur.

Subjects will be analyzed according to the trial treatment received, as defined for the FAS.

5 General Statistical Methods and Definitions

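### The SAP ends the DLT window at Day 21, but protocol 7.1 and 11.1.7 end it 7 days after the first full dose, so a DLT after a delayed first full dose can go uncounted

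*SAP*

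**What the plan says.** SAP 5.5 defines the window in one sentence: "For the Escalation Part only, the DLT period is defined as the first 21 days of treatment, as per protocol 7.1". It then runs from Cycle 1 Day 1 to Cycle 1 Day 21, with no provision for a late dose or a second intermediate dose.

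SAP section 4 builds the dose-determining set (DDS) on the same 21 days. A subject qualifies through a DLT if they "experience a DLT during the first 21 days of dosing (i.e., in Cycle 1". A subject without a DLT needs at least 21 days of observation from the first dose, a joint sponsor and investigator judgement that the safety data are sufficient, and minimum exposure. Exposure is met if the subject "takes at least 2 out of 3 pre-planned doses during the DLT period". SAP 9.1 summarises DLTs on the DDS and counts only events inside the DLT period.

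Protocol 7.1 defines the period from the first administration to 7 days after the first full dose, and gives the lengths that follow:

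- One intermediate dose, full dose from C1D15: "the DLT period will be the first 21 days of Cycle 1 (Cycle 1 days 1 through 21".
- Two intermediate doses, first full dose on C2D1: "the DLT period will be Cycle 1 up to and including C2D7 (ie, a total of 28 days".
- Delay: "The DLT evaluation period may be adjusted for potential GEN1044 treatment delay as described in Section 11.1.7".

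Protocol 11.1.7 repeats the 7-day rule and requires every dose up to and including the first full dose. It tolerates delay within limits: "In general, the individual doses should not be delayed more than 7 days", and "The first full dose should be administered at latest by 30 calendar days after C1D1" with one intermediate dose (38 calendar days with two).

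SAP 1.2 names protocol v4.0 among its sources (beside v3.0), and SAP 2.1 declares only a change to the efficacy reporting.

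**The concern.** The SAP cites protocol 7.1 for a rule that 7.1 gives only as its on-schedule, one-intermediate case. The two documents agree when the first full dose falls on Day 15 and part company as soon as it falls later. The window exists to capture toxicity in the week after the first full dose, and that is the part the SAP shortens.

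DLTs are the primary endpoint of the escalation part. An event that is a DLT under the protocol can drop out of the reported summary while the subject stays in the denominator, which understates the rate. Delays need not be unrelated to toxicity, because protocol 7.2.1 lets a dose be postponed for an adverse event.

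Other SAP text suggests carry-over from before Amendment 3 rather than a deliberate choice. SAP 3.2 still plans up to 58 subjects where protocol 4.4 plans about 80. SAP section 4 illustrates 2 of 3 doses with a priming dose and a full dose, which suits a schedule without an intermediate dose.

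**Working it through.** **Inputs.** The protocol window ends 7 days after the first full dose (7.1, 11.1.7). The SAP window ends on Day 21 (5.5). The C1D15 visit window is +1 day (protocol Table 1). The ordinary delay allowance is 7 days per dose, and the outer limit with one intermediate dose is about Day 30 (11.1.7).

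**Reproducing the protocol's figures.** Let *d* be the study day of the first full dose, counted as the first of the 7 days. The protocol window ends on Day *d* + 6. For *d* = 15 this is Day 21, and for *d* = 22 (C2D1) it is Day 28. Both match 7.1.

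**Full-dose days inside the SAP window**, for *d* of 15 or more: max(0, 22 − *d*), out of 7.

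| First full dose (*d*) | Situation | Protocol window ends | Full-dose days in SAP window | Days lost after Day 21 |
|---|---|---|---|---|
| 15 | on schedule | Day 21 | 7 | 0 |
| 16 | within the +1 day visit window | Day 22 | 6 | 1 |
| 17 to 21 | shorter delays | Day 23 to 27 | 5, 4, 3, 2, 1 | 2 to 6 |
| 22 | 7-day delay (15 + 7) | Day 28 | 0 | 7 |
| 30 | outer limit, one intermediate dose | Day 36 | 0 | 15 |

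If the outer limit is read as Day 31, the last row becomes Day 37 and 16 days.

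**Does the DDS rule catch it?** Take priming on Day 1, intermediate on Day 8 and first full dose on Day 22.

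- Under 11.1.7 the delay is 7 days and the first full dose was given, so the exposure criterion is met. A DLT on Days 22 to 28 counts.
- Under SAP section 4, 2 of 3 planned doses were taken by Day 21 and 21 days were observed, so both numerical minimums are met with no full-dose day seen. If the data are judged sufficient, the subject enters as DLT-free, and SAP 9.1 excludes a DLT on Days 22 to 28 by date.
- By the same rule, a subject who never received a full dose could enter the SAP's DDS.

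**Which cohorts.** SAP Table 1 lists nine:

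- Six reach the full dose at C1D15 (1/3/10, 1/3/30, 1/5/30, 1/10/30, 1/5/45, 1/3/60) and are exposed through delays. The footnote to 1/5/45 is not in the text available.
- Two (0.3/3/3, 1/5/5) have a C1D8 dose equal to the later ones. Read literally, the 7.1 rule ends on Day 8 + 6 = 14, so the SAP window is 21 − 14 = 7 days longer there.
- One (1/5/30/37.5) shows its C1D15 and C2D1 doses in brackets and cannot be judged.

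**Effect of one omitted DLT.** The rate falls by 1/*n*: 1/3 = 33 percentage points, 1/6 = 17, 1/10 = 10. These values of *n* are assumed. Ten is the maximum dose-level cohort size in protocol 4.2.1.1. The documents give no evaluable counts per cohort.

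**The case against.** The strongest reply is that the SAP applies the branch that was used. SAP 1.2 says at most one intermediate dose was tested, and 7.1 gives 21 days for that schedule. This holds for on-schedule subjects, and it means the 28-day branch may affect no one. It does not cover delayed subjects.

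The protocol is also not uniform. Section 4.2 gives 21 days from the priming dose (28 with two intermediate doses), 4.2.1.1 refers to a 21-day period, and the minimum follow-up in 11.1.7 is itself 21 days from priming. The delay adjustment in 7.1 is permissive. That is fair, and SAP section 4 shares its 21-day follow-up with 11.1.7. But 11.1.7 pairs that figure with a requirement that the first full dose was given, which the SAP drops, and the section the SAP cites is 7.1.

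The sponsor and investigator judgement is a real check on who enters as DLT-free. It cannot restore an event that SAP 9.1 excludes by date.

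A literal per-subject window would stop at Day 14 for 0.3/3/3 and 1/5/5 and could drop events on Days 15 to 21. This objection stands, so those cohorts need an explicit rule. Protocol v3.0, which may have governed them, is not available here.

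Finally, no delayed subject or late DLT is documented. Enrolment has stopped, dose decisions rested with the Dose Escalation Committee and Safety Committee, and late events would still appear in the treatment-emergent tables. This limits the consequence to the DLT summary and DDS in the abbreviated report, where DLTs remain the primary endpoint.

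**Conclusion.** The concern holds. The SAP misstates the protocol section it cites, and neither its fixed window nor its looser exposure rule is declared as a change. Coverage of the 7 full-dose days falls from 7 on schedule to 0 at the ordinary 7-day delay allowance. At the outer limit the protocol window closes about 15 days after the SAP's.

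This rests on counting the first-full-dose day as the first of the 7, which reproduces the protocol's own 21 and 28 days. The actual number of omitted DLTs is unknown and may be zero. The 33, 17 and 10 percentage-point figures show what one omission would do at assumed cohort sizes. It should be corrected before the report is produced. It does not reopen past dose decisions.

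**What to change.** In SAP 5.5 and section 4:

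- Replace the fixed 21 days with the protocol 7.1 and 11.1.7 definition, derived per subject from the actual date of the first full dose, including the 28-day branch in case it applies.
- Require a DLT-free subject to have been followed to that date.
- Replace the 2-of-3 rule with the 11.1.7 exposure criterion.
- State how cohorts at full dose from C1D8 are handled, so that the change does not shorten their window by default.

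If a fixed 21-day window is intended, declare it and the 2-of-3 rule in SAP 2.1 as changes from protocol v4.0. Also list DLT-type events between Day 21 and the end of the protocol window.

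The protocol's remaining fixed-day wording should be reconciled with the 7.1 definition: the day counts from priming in 4.2 and 11.1.7, the 21-day reference in 4.2.1.1, and the Cycle 1 discontinuation criterion in 7.1. With enrolment stopped this adds little, and a statement in the SAP of which wording governs the analysis would serve.

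The cost on the SAP side is revised text and one re-derived date variable. Some subjects may change DLT or evaluability status, and the DDS may become smaller.
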